5.2.2 Blinding procedures

The examiner and radiologist will be blinded to the intervention. The intervention administrator will be blinded to the result of the patient examination and MRI. Patient blinding to intervention is not possible due to the nature of SMT.

5.2.3 Other methods of minimizing bias

The use of standardized protocols for data collection and training of study personnel will minimize interobserver variability. Validated questionnaires (painDetect and ODI) will be used to assess pain qualities and pain-related disability to minimize wording bias.

5.3 Unblinding procedures (Code break)

Unblinding will be done only for the purpose of data interpretation after the inclusion of the last partic-

ipant.

6. STUDY POPULATION

6.1 Eligibility criteria

Inclusion criteria:

Patients:

- a) **Persons over 18 years and under 75 years of age with low back pain of any duration clinically not attributable to “red flags” (infection, trauma, fractures, inflammatory illnesses).**
- b) **Source of LBP clinically at the L4/5 or L5/S1 segment.**
- c) Duration of LBP is longer than 4 weeks
- d) **Obtained informed consent.**

Controls:

- a) Persons over 18 years and under 75 years of age who have not suffered from low back pain in the last year and have never experienced low back pain for longer than 7 consecutive days.
- b) Obtained informed consent.

Exclusion criteria:

Subjects are excluded from enrolment if they

- a) **have undergone prior spinal surgery**
- b) **have undergone facet joint, epidural or periradicular injections in the last 6 months**
- c) had a spinal manipulative therapy intervention in the past 2 weeks
- d) **have spinal abnormalities (benign or malignant tumors, congenital abnormalities, isthmic spondylolisthesis)**
- e) **have any contraindication to spinal manipulative interventions or are deemed unable to tolerate SMT to both body sides (e.g. pain attributable to above mentioned red flags, inability to perform side-lying without pain, radiculopathy with motor deficits <M4-, severe spinal canal stenosis)**
- f) **have any contraindication to MRI (e.g. heart pacemaker, metallic foreign body or claustrophobia)**
- g) have started a new prescription medication targeting blood circulation within the last 3 months
- h) **are pregnant or nursing**
- i) Subjects are excluded from venipuncture if they are known to be HIV-positive or have Hepatitis A, B, or C or have another systemic infection (excludes subjects from venipuncture). No study specific testing for HIV or Hepatitis A, B or C is performed.

6.2 Recruitment and screening

Patients will be recruited from within the Department of Chiropractic Medicine at the University Hospital of Balgrist.

Asymptomatic controls will be recruited by flyers displayed on the hospital's internal website (intranet) and notice boards.

6.3 Assignment to study groups

Patients are subdivided into strata in order to match for age, sex, and degenerative changes, then permuted

block randomization is used for each stratum to assign patients to receive either SMT or control intervention. Randomization is performed by an investigator not involved in the examination using sequentially numbered sealed opaque envelopes.

6.4 Criteria for withdrawal / discontinuation of participants

Subjects are excluded from enrolment due to

- a) **withdrawal of informed consent**
- b) non-compliance
- c) the safety of the participant being doubtful or at risk, respectively
- d) contraindications to SMT determined on the first study MRI
- e) the necessity of a spinal manipulative intervention, spinal corticosteroid or anaesthetic infiltrations or spinal surgery after inclusion into the study and before the study visit

If pregnancy cannot be ruled out with certainty, female patients of child-bearing age are tested for pregnancy prior to the MRI examination using a urine pregnancy test.

If consent is revoked, the health-related personal data of the person concerned will be anonymized after data evaluation has been completed.

7. STUDY INTERVENTION

7.1 Identity of Investigational Treatment

7.1.1 Experimental Intervention

The patient turns from supine to right-side lying position, is positioned by the chiropractor administering the intervention, and receives a spinous push-pull SMT intervention as described by Bergman et al. at the previously marked segment³⁶. Specifically, the patient lies in side-lying position, with the hip of the up-side leg flexed to ca. 90° and the foot of the flexed leg hooked behind the popliteal space of the down-side leg. The chiropractor stands facing the subject at a 45°-angle, fixating the flexed knee with his own knee/thigh. The fingertips of the cephalic hand reach under the patient's up-side arm to contact the up-side lateral surface of the superior spinous process. The fingertips of the caudal hand hook the inferior spinous process, contacting the down-side aspect of the spinous process, while the forearm contacts the patient's posterolateral buttock and thigh. The cephalic hand thrusts lateromedially and caudocranially, from up-side toward down-side ("push"). The caudal hand thrusts lateromedially in the opposing direction, from down-side toward up-side, toward the chiropractor ("pull"). The SMT intervention is repeated after the patient turns to left side lying. The patient then resumes supine position.

7.1.2 Control Intervention

The patient turns from supine to right-side lying position and is positioned with the hip of the up-side leg flexed to ca. 90° and the foot of the flexed leg hooked behind the popliteal space of the down-side leg. The chiropractor stands facing the subject at a 45°-angle, fixating the flexed knee with his own knee and placing both hands as described for the experimental intervention. No pressure, preload or thrust is administered. This intervention is repeated after the subject turns to left side lying. The subject then resumes supine position.

7.1.3 Packaging, Labelling and Supply (re-supply)

Not applicable.

7.1.4 Storage Conditions

Not applicable.

7.2 Administration of experimental and control interventions

7.2.1 Experimental Intervention

The experimental intervention will be administered as described in chapter 8.1.1. The experimental procedure

will take place in the University Hospital Balgrist

7.2.2 Control Intervention

The control intervention will be administered as described in chapter 8.1.2. The experimental procedure will take place in the University Hospital Balgrist.

7.3 Dose / Device modifications

Not applicable.

7.4 Compliance with study intervention

Not applicable.

7.5 Data Collection and Follow-up for withdrawn participants

The data of withdrawn participants is going to be excluded from the final analysis.

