8.2.5 Assessments in participants who prematurely stop the study

Patients who are withdrawn from the study prematurely are routinely scheduled for a follow-up visit after 4-6 weeks. Recording of adverse events, physical examination and vital signs is going to be performed according to the standards of the University Hospital Balgrist. Data of withdrawn patients is not going to be considered in the final analysis.

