10.3.1 Dataset to be Analysed, analysis populations

The statistician will supervise the analysis as described in 11.4.

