10.4 Handling of missing data and drop-outs

Intention to treat analysis is planned to account for missing data.

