11.5 Confidentiality, Data Protection

Direct access to source documents will be permitted for purposes of monitoring (12.3), audits and inspections (12.4). Only authorised medical personnel are going to have access to protocol, dataset and statistical code during and after the study.

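### Sections 7.5 and 8.2.5 drop every withdrawn participant from the final analysis, although 10.4 plans intention to treat and the primary scans are complete at Visit 2

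*Combined protocol and SAP*

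**What the plan says.** Two sections on trial conduct remove withdrawn participants. Section 7.5: "The data of withdrawn participants is going to be excluded from the final analysis". Section 8.2.5: "Data of withdrawn patients is not going to be considered in the final analysis". Neither refers to the time of withdrawal or to whether the scans already exist.

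The statistics chapter says otherwise. Section 10.4: "Intention to treat analysis is planned to account for missing data". Section 10.3.1, whose heading promises the analysis populations, has one sentence: "The statistician will supervise the analysis as described in 11.4". Section 11.4 is about audits and inspections.

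Section 6.4 lists the withdrawal criteria but opens with "Subjects are excluded from enrolment due to". Its reasons are revoked consent (a), non-compliance (b), doubtful safety (c), a contraindication seen on the first MRI (d), and certain treatments needed before the study visit (e). It also provides that after consent is revoked, personal health data are anonymised once data evaluation is finished. Section 7.4, on compliance with the intervention, is marked not applicable.

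**The concern.** The primary outcome (4.1) is the MRI change from before to after the intervention. Under 5.1 and 8.3.2, the baseline scan, randomisation, intervention and post-intervention imaging of patients all take place at Visit 2. Under 8.3.3, patients remain in the study until the three-month questionnaire. For about 90 days after the primary measurement is complete, a formal withdrawal would delete it under 7.5 and 8.2.5.

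That is an exclusion after randomisation. Section 5.2.2 says patients cannot be blinded, so withdrawal may depend on arm and on how the patient felt afterwards. Section 3.4 cites an earlier study in which pain response after manipulation was related to disc diffusion, so a link between withdrawal and the primary outcome is plausible. Blinding the examiner and the radiologist does not prevent this. With two incompatible rules on file, the analysis set could also be chosen after the data are seen, unless an amendment settles it first.

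**Working it through.** **1. Do the passages reconcile?**

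- *Cross-reference.* The pointer in 10.3.1 to 11.4 is most plausibly a slip for 10.4. Other references are also one chapter too high: 7.2.1 and 7.2.2 cite 8.1.1 and 8.1.2 for procedures found in 7.1.1 and 7.1.2, and 11.5 cites 12.3 and 12.4 for 11.3 and 11.4. Read this way, 10.3.1 leads to the single sentence in 10.4, which neither defines intention to treat nor overrides 7.5 and 8.2.5.
- *Timing in 6.4.* Reasons (d) and (e) precede randomisation. Reasons (a) to (c) carry no time limit, and non-compliance is not defined.
- *Section 8.2.5.* It schedules withdrawn patients for follow-up after 4 to 6 weeks with recording of adverse events, which 9.1.1 defines as occurring after an intervention. This suggests that withdrawal after treatment is foreseen.
- *Revoked consent.* Anonymising only after evaluation implies that the data are used, which conflicts with 7.5.

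The texts do not reconcile.

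**2. The plan's own power figure (10.2).** Inputs: 25 per group, effect 0.9 (read as standardised), alpha 0.05 (two-sided assumed), stated power 0.8. For a two-sample t test with n per arm, the noncentrality is 0.9 × √(n/2) on 2n − 2 df. At n = 25 this is 0.9 × √12.5 = 3.18 on 48 df, against a critical value of 2.011, so power is 0.877. The stated 0.8 does not reproduce, since 21 per arm would suffice. The plan is on the large side, and the present point does not depend on this.

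**3. Power if withdrawn patients are dropped.** The numbers lost are assumptions. The second column uses 2n − 4 df, for the planned ANOVA with equal degeneration groups assumed. The third takes 0.80 at 25 per arm as the true starting point, which needs an effect of 0.809.

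| Per arm | Effect 0.9, t test | Effect 0.9, ANOVA df | Effect 0.809, t test |
|---|---|---|---|
| 25 | 0.877 | 0.876 | 0.800 |
| 24 | 0.863 | 0.862 | 0.783 |
| 22 | 0.831 | 0.830 | 0.746 |
| 21 | 0.812 | 0.811 | 0.725 |
| 20 | 0.792 | 0.791 | 0.703 |

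Loss from one arm only, effect 0.9: 24 v 25 gives 0.870 and 23 v 25 gives 0.862.

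**4. Shift in an arm mean.** Removing k of 25 patients, each z SD from the arm mean, moves that mean by kz/(25 − k). For k = 1: z = 1 gives 1/24 = 0.042 SD, and z = 2 gives 2/24 = 0.083 SD. For k = 2, z = 1: 2/23 = 0.087 SD.

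**5. Selective loss, illustration only.** The null is true, with 200,000 simulated trials per cell. The k patients in the SMT arm with the lowest withdrawal score are removed. The pain–diffusion correlation is assumed to be 0.3 or 0.5, as the documents give no coefficient.

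| Withdrawal score | k | Bias in SD (0.3 / 0.5) | Type I error (0.3 / 0.5) |
|---|---|---|---|
| Correlates 0.5 with pain response | 1 | 0.012 / 0.020 | 0.050 / 0.051 |
| Correlates 0.5 with pain response | 2 | 0.022 / 0.037 | 0.050 / 0.053 |
| Equals pain response | 1 | 0.025 / 0.041 | 0.051 / 0.053 |
| Equals pain response | 2 | 0.046 / 0.077 | 0.054 / 0.061 |

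Loss from the control arm gives the same size with opposite sign (−0.046 / −0.076 for the last row). Bias is zero if loss is unrelated to outcome, or if both arms lose equal numbers by the same mechanism. Equal numbers alone are not enough: with two lost per arm, correlation 0.5, worst responders leaving one arm and best responders the other, bias is 0.15 SD and type I error 0.086.

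**The case against.** The strongest reply is that 7.5 can be read narrowly. If 11.4 means 10.4, the statistics chapter does name intention to treat. The only list of withdrawal criteria opens with exclusion from enrolment, so 7.5 may be meant for people who never reach randomisation. That reading is available, but the text does not secure it: reasons (a) to (c) have no time limit, and 8.2.5 fits withdrawal after treatment.

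The second reply is that few patients are exposed. After Visit 2 only questionnaires or calls remain, and a missed questionnaire or later treatment is not called withdrawal. Non-compliance and safety have little left to act on, so revoked consent is the realistic route. The consent pages, which are not in our copy, may govern those data. This stands, and it keeps the point modest, but consent rules would not settle reasons (b) and (c).

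Third, the calculated harm is small. The upper end needs the two worst responders to leave one arm only, with an assumed correlation of 0.5. This also stands.

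Fourth, a set that requires a post-intervention scan is itself a restriction made after randomisation. That is correct, and the fix labels the set accordingly.

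**Conclusion.** The contradiction is certain on the text. As written, 7.5 and 8.2.5 would delete complete primary data from randomised, unblinded patients, against the principle in 10.4. It should be fixed, but the likely harm is limited. At effect 0.9, power falls below 0.80 only when about five per arm are lost. If true power starts at 0.80, one lost per arm gives 0.783 and four give 0.725. Illustrated bias for one or two losses from one arm is 0.01 to 0.08 SD, upward if the loss is in the SMT arm and downward if in the control arm, with type I error up to 0.061. It is larger only if the two arms lose opposite kinds of patient. If withdrawal is unrelated to outcome, the only cost is power. All of this rests on assumed numbers lost and an assumed pain–diffusion correlation.

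**What to change.** - **7.5 and 8.2.5:** limit the exclusion to participants withdrawn before randomisation. State that data collected before a later withdrawal are kept and analysed as consent permits. For the non-randomised controls, keep any complete pair of scans.
- **10.3.1:** correct the reference to 10.4. Define the primary set as all randomised patients, analysed in the arm assigned, with a baseline and at least one post-intervention MRI, whether or not they withdraw later. Call this modified intention to treat. List randomised patients without a post-intervention MRI by arm and reason.
- **6.4:** say for each reason whether it applies before or after randomisation, what non-compliance means for the analysis, and how data are used once consent is revoked. Check this against the consent form.
- **Optional:** report the analysis without withdrawn patients as a sensitivity analysis only.

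The cost is an amendment to the wording of four sections and a check of the consent form, with no extra patients or data. It should be in place before outcome data are examined by arm.

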7.6 Trial specific preventive measures

[figure not shown]
Not applicable

7.7 Concomitant Interventions

Patients requiring spinal manipulative interventions, spinal corticosteroid or anaesthetic infiltrations as well as spinal surgery between inclusion into the study and the study visit are excluded from the study. After the study visit, type and frequency of concomitant interventions will be assessed by telephone interviews at one week and one and three months after the study visit.

8. STUDY ASSESSMENTS

8.1 Study flow chart(s) / table of study procedures and assessments

8.2 Assessments of outcomes

8.2.1 Assessment of primary outcome

Diffusion and perfusion parameters on DWI and IVIM-MRI are determined by an experienced radiologist at the University Hospital of Balgrist.

8.2.2 Assessment of secondary outcomes

Diffusion and perfusion parameters on DWI and IVIM-MRI in controls are also determined by an experienced radiologist at the University Hospital of Balgrist.

8.2.3 Assessment of other outcomes of interest

Clinical baseline parameters and change in pain intensity on a numerical pain rating scale after intervention will be assessed by an investigator blinded to the radiological information and the administered intervention. Classification of degenerative changes on MRI are determined by an experienced radiologist at the University Hospital of Balgrist.

Patients who consent to giving a blood sample will have venipuncture performed by a medical professional trained in the procedure.

8.2.4 Assessment of safety outcomes

Patients' vital signs and pain intensity will be assessed before and after the experimental procedure and recorded according to clinical standards. The patient will be able to verbally communicate discomfort or pain at any time during the experimental procedure.

8.2.4.1 *Adverse events*

Time of onset, duration, resolution, action to be taken, intensity and relationship with SMT intervention of adverse events are going to be recorded according to clinical standards. Participants are going to be assessed for adverse events according to current standard of care after the experimental procedure.

8.2.5 Assessments in participants who prematurely stop the study

Patients who are withdrawn from the study prematurely are routinely scheduled for a follow-up visit after 4-6 weeks. Recording of adverse events, physical examination and vital signs is going to be performed according to the standards of the University Hospital Balgrist. Data of withdrawn patients is not going to be considered in the final analysis.

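### Sections 7.5 and 8.2.5 drop all data of withdrawn participants, against intention to treat in 10.4, and 10.3.1 defines no analysis set

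*Combined protocol and SAP*

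**What the plan says.** Two sections remove withdrawn participants. Section 7.5: "The data of withdrawn participants is going to be excluded from the final analysis". Section 8.2.5, for patients: "Data of withdrawn patients is not going to be considered in the final analysis". Neither limits the rule by when the withdrawal happens or by what has already been measured.

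Section 10.4 reads: "Intention to treat analysis is planned to account for missing data". It names no method for a missing value.

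Section 10.3.1, whose heading announces the dataset and analysis populations, contains one sentence: "The statistician will supervise the analysis as described in 11.4". It defines no set.

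Section 6.4 lists the withdrawal grounds under the lead-in "Subjects are excluded from enrolment due to". They are a) revoked consent, b) non-compliance, c) "the safety of the participant being doubtful or at risk, respectively", d) "contraindications to SMT determined on the first study MRI" and e) the need for certain spinal treatments, up to "spinal surgery after inclusion into the study and before the study visit". The same section has the data of a person who revokes consent anonymised once evaluation is finished.

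**The concern.** The primary analysis in 10.3.2 compares the SMT and control-intervention arms, and that comparison rests on randomisation. If patients who leave after randomisation are removed together with the scans they already have, the groups compared are formed partly by events after assignment. Patients know which procedure they received (5.2.2), and only SMT includes a thrust (7.1.1, 7.1.2), so reasons for leaving could differ by arm.

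The plan also gives two answers to one question. An analyst following 7.5 and an analyst following 10.4 would analyse different patients, and nothing says which rule prevails. With 25 patients per arm, that should be settled before the data are seen.

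Controls are affected too. Section 4.1 puts their change over 20 minutes of supine rest in the primary outcome. A control who withdraws before the 10-hour scan would lose a completed repeat pair under 7.5.

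**Working it through.** **1. Which withdrawals are affected**

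- Grounds d) and e) in 6.4 act before randomisation: the first MRI precedes randomisation in 8.3.2, and e) is limited to the time before the study visit. Excluding these patients does not conflict with intention to treat.
- Grounds a), b) and c) carry no time limit.
- Randomisation, procedure and post-intervention imaging all take place at Visit 2 (8.3.2). A patient's study ends only at three months (8.3.3).
- A patient withdrawn under a), b) or c) during follow-up therefore already has the primary outcome, and 7.5 and 8.2.5 as worded discard it. The plan does not say this outright; it follows from the unqualified exclusion and the visit schedule.
- Section 7.7 records concomitant treatment after the visit and does not exclude for it, so that route is closed.
- For revoked consent, 6.4 anonymises only after evaluation, which implies that the data are evaluated. Section 7.5 thus conflicts with 6.4 as well as with 10.4.

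**2. Size of the error (illustration)**

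From the plan (10.2): 25 patients per arm and an expected ADC increase of 6.5% after SMT. Assumed: k = 1, 2 or 3 SMT patients are withdrawn and discarded, the remaining SMT patients average 6.5%, and the discarded ones have true change r.

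Error in the SMT mean = (k/25) × (6.5 − r). The full-arm mean is 6.5 minus that error.

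| r | k = 1 | k = 2 | k = 3 |
|---|---|---|---|
| 0% | +0.26 (mean 6.24; +4.2%) | +0.52 (5.98; +8.7%) | +0.78 (5.72; +13.6%) |
| 6.5% | 0 | 0 | 0 |
| 13% | −0.26 (6.76; −3.8%) | −0.52 (7.02; −7.4%) | −0.78 (7.28; −10.7%) |

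Errors are in percentage points. Withdrawals from the control-intervention arm would add an error of their own.

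For scale, assume that 6.5% corresponds to the effect of 0.9 in 10.2. Then SD = 6.5/0.9 = 7.2 points, the standard error of the difference = 7.2 × √(2/25) = 2.0 points, and the largest error shown is 0.78/2.0, about 0.4 standard errors.

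**3. Power**

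The plan's own figure is 0.80 for 25 per group, effect 0.9 and alpha 0.05. Reading 0.9 as a standardised difference, a two-sided two-sample t-test gives 0.877; 21 per group would reach 0.80. The stated figure does not reproduce, but the difference is on the safe side.

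Now suppose that k withdrawn SMT patients are kept, that they have zero response, and that 0.9 is the effect in the others. With p = k/25, the mean difference is 0.9(1 − p), the SMT variance is 1 + 0.81p(1 − p), and the effective d is the difference divided by the pooled SD.

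| k | difference | pooled SD | effective d | power, kept | power, dropped |
|---|---|---|---|---|---|
| 1 | 0.864 | 1.008 | 0.857 | 0.844 | 0.870 |
| 2 | 0.828 | 1.015 | 0.816 | 0.807 | 0.862 |
| 3 | 0.792 | 1.021 | 0.776 | 0.766 | 0.854 |

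Simulation with exactly k zero-responders gives 0.847, 0.810 and 0.770. The t-test stands in for the planned ANOVA.

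**The case against.** The best defence is that the situation will hardly arise. The lead-in to 6.4 speaks of enrolment, and d) and e) act before randomisation. The procedure is given once, at the same visit as the repeat scan. Afterwards patients only answer questionnaires, so no intervention is left to stop for safety. Section 7.4 marks compliance as not applicable, and nothing says that a missed questionnaire counts as withdrawal. This stands as a limit on exposure. It does not remove the conflict: a) to c) have no time limit, 7.5 and 8.2.5 have no exception, and 8.2.5 provides a follow-up visit at 4 to 6 weeks for patients who stop early.

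It can also be said that intention to treat is plainly meant. The pointer in 10.3.1 to 11.4 lands on audits and inspections. Other cross-references are one chapter too high (7.2.1 sends the reader to 8.1.1 for text found in 7.1.1), so 10.4 may be the target. Even so, 10.4 defines no set and does not override 7.5.

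A reader might infer that the rule favours SMT. The documents do not support that: control-intervention patients may leave too, and nothing indicates how those who leave respond. A reader might also infer a serious false-positive risk. With no true effect, and the two lowest-change SMT patients being the ones removed, simulation gives a bias of about 0.15 SD and a two-sided type I error of about 0.10. That is a deliberately extreme case; nothing says patients learn their ADC change.

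Finally, the dilution figures hold only if withdrawn patients do not respond and 0.9 excludes them. If 0.9 is already the average over all randomised patients, keeping them does not lower power in that way.

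**Conclusion.** The conflict is real and lies in the operative text: 7.5 and 8.2.5 against 10.4 and 6.4, with 10.3.1 silent. Followed literally, the exclusion rule would discard acquired post-intervention scans of randomised patients and break the comparison as randomised. It should be corrected.

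The practical exposure is probably small. In the illustration the error is at most 0.78 percentage points either way, and it rests on assumed withdrawal counts and responses. The conclusion does not depend on those figures; it rests on the wording and on the visit schedule. Loss of power is secondary: at d = 0.9, even four exclusions per arm leave 21 per arm and power of 0.812.

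**What to change.** Replace the sentence in 7.5 and the last sentence of 8.2.5, and state the same in 10.3.1:

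> Patients removed before randomisation (including 6.4 d and e) are not analysed. Every randomised patient is kept in the assigned arm, and all data acquired up to withdrawal are used, including after revoked consent as 6.4 provides, unless the law or the consent form forbids it. The primary ANOVA includes every randomised patient with a pre- and a post-intervention MRI; randomised patients without a post-intervention MRI are reported by arm with reasons. Controls' data acquired before withdrawal are used, including a completed 20-minute repeat pair when the 10-hour scan is missing.

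The third sentence is needed because intention to treat does not say how a patient with only a baseline scan enters a pre/post ANOVA. Such patients still drop out of that analysis, so their number and reasons must be visible by arm. The 4 to 6 week visit in 8.2.5 stays, and safety decisions remain with the investigator.

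The cost is protocol wording; no scan or patient is added. The downside is possible dilution if retained patients respond less. Under the zero-response assumption above, three retained patients would take power to about 0.77, below the planned 0.80. Dropping them would hold power at about 0.85, but only by changing who is compared.
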